1.0 INTRODUCTION

In developed countries, approximately 20–25% of pregnant women will require labour induction (IOL) for various indications. (1) In considering IOL the benefits of an earlier delivery should outweigh the risks of continuing the pregnancy.(2) An unripe cervix is a risk factor for failed IOL and Caesarean delivery whereas prior vaginal delivery has the opposite impact. (3)

The two major techniques for cervical ripening are mechanical intervention and the use of pharmacologic agents.(4) Mechanical dilatation of the cervix may be via the transcervical placement of the single balloon catheter (i.e., Foley catheter). the double balloon catheter (i.e. Cook or Atard catheter) or with the use of osmotic dilator such as natural compound Laminaria, or synthetic compounds such as Lamicel and Dilapan.(5) Pharmacological forms of induction include prostaglandins and oxytocin.(6, 7) World Health Organization (WHO) strongly recommends the use of balloon catheter for induction of labor(8).

A lengthy induction process can increase adverse outcomes(1, 4, 9) and the burden on health care resources(10). Hence, it is clinically important to find an induction protocol that is efficient in order to reduce interval to delivery which in turn may increase maternal satisfaction.

Mechanical induction particularly with the single-balloon Foley catheter is widely used as the primary IOL method when cervical ripening is needed due to its low cost and reduced likelihood of uterine hyperstimulation compared to prostaglandins.(11) Studies have compared balloon catheter placement for 12 vs 24 hours finding that 12-hour placement results in shorter interval to delivery. (12, 13)

A recent study comparing 6 vs 12 hours placement with the double-balloon catheter has also shown reduction in the interval to delivery with the shorter placement period without increment in caesarean section rate. (14) Similarly, another study conducted using the double balloon catheter also but with only a single balloon inflated also shows shorter interval to delivery time in the 6-hour arm compared to the 12-hour group.(15) Both above-mentioned study used the costly double-balloon catheter. A 2017 meta-analysis (five randomized trials: 996 women) published in 2017, comparing single with double-balloon catheters for IOL shows the time from catheter insertion to delivery did not differ between the two types of catheters.(16)

A 2018 systematic review on complications from insertion to expulsion of a balloon catheter during labor induction reports adverse event rates of 0.0-0.26% with 'pain/discomfort' having the highest prevalence.(17) Foley induction ripens the cervix and progression to labour is uncommon without amniotomy and oxytocin augmentation.(18)

The aim of the present study is to compare the planned removal after 6 vs 12 hours placement of the Foley catheter in multiparas with unripe cervices scheduled for IOL with the hypothesis that the 6-hour arm will have a shorter interval to delivery and higher patient satisfaction with the induction process.

2.0 OBJECTIVE OF THE STUDY

The purpose of the study is to evaluate whether removal of foley's catheter after 6 hours compared to 12hours in multiparous women undergoing induction of labour will result in a shorter duration of intervention to delivery time and increase maternal satisfaction with the induction process.

3.0 RESEARCH HYPOTHESIS

We hypothesise that induction of labour with foley's catheter removed at 6 hours compared to 12 hours will result in a shorter interval to delivery and increase maternal satisfaction.

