4.5 SAMPLE SIZE CALCULATION

To calculate our sample size for the primary outcome, we obtained data from literature review on:

Primary outcome 1: Induction to delivery interval

Bleicher et al reported mean induction to delivery interval in the multiparous subgroup for 6 hours vs 12 hours double balloon placement as 18.0 hours with SD 6.8 vs 22.6 hours SD 8.2, p= 0.04 respectively, a mean reduction of 4.6 hours in favour of 6-hour placement.(14)

Using https://www.openepi.com/SampleSize/SSMean.htm and applying alpha of 0.02 (Bonferroni correction for 2 primary outcomes), t test, 80% power, 1 to 1 ratio, 18.0 hours with SD 6.8 vs 22.6 hours SD 8.2, 54 women are required per arm (total 104). Factoring in the possibility of non-normal data distribution requiring Mann Whitney U test application, we increase sample size by 15% and assuming 10% dropout, we plan to recruit $54 \times 1.15/0.9 = 69$ in each arm (N = 138 women)

For maternal satisfaction, assuming a 1-point difference in the 11-point 0-10 visual numerical rating scale (VNRS) to be clinically relevant. Using https://www.openepi.com/SampleSize/SSMean.htm and applying alpha of 0.02 (Bonferroni correction for 2 primary outcomes), t test, 80% power, VNRS standard deviation of 2 for both arms, 81 women are required per arm (total 162). Factoring in the Mann Whitney U test application as satisfaction score is ordinal, we increase sample size by 15% and assuming 10% dropout, we plan to recruit $81 \times 1.15/0.9 = 103.5$ in each arm (total of 207 women). We rounded the required sample size of participants up to N = 210 in total to adequately cover for both primary outcomes.

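### The two primary outcomes are sized under single-step Bonferroni at 0.02 each, which is valid but gives up power that Holm's procedure would recover with the same 210 women

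*Protocol*

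**What the plan says.** The aim in the Introduction, the objective (Section 2.0) and the hypothesis (Section 3.0) each name both outcomes in one sentence. Section 3.0 expects that 6-hour removal "will result in a shorter interval to delivery and increase maternal satisfaction". Section 5.0 lists the two as primary outcomes.

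Section 4.5 calculates a sample size for each outcome on its own, in both cases "applying alpha of 0.02 (Bonferroni correction for 2 primary outcomes), t test, 80% power". For the interval it uses "18.0 hours with SD 6.8 vs 22.6 hours SD 8.2, 54 women are required per arm". For satisfaction it proceeds by "assuming a 1-point difference in the 11-point 0-10 visual numerical rating scale (VNRS) to be clinically relevant", takes an SD of 2 in both arms and arrives at 81 per arm. Each figure is raised by 15% for the Mann-Whitney test and divided by 0.9 for dropout. The larger result is rounded up to a total of 210 "to adequately cover for both primary outcomes".

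Section 6.1 names the tests but gives no significance level and no order of testing. Bonferroni at 0.02 is therefore the only multiplicity method that the protocol names.

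**The concern.** Single-step Bonferroni keeps each outcome at its reduced level whatever happens to the other. Here that is wasteful. Satisfaction needs 81 women per arm against 54 for the interval, so at the chosen size the interval has ample power and will usually succeed if the assumptions hold. Its share of alpha could then pass to satisfaction, but under the named method it is not used.

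A concrete case: the interval is clearly significant and satisfaction has p = 0.03. At 0.02 per outcome, satisfaction is declared negative. Under Holm at family alpha 0.05 it is validly declared positive, because the interval has passed at 0.025 and 0.03 lies below 0.05.

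The protocol words its hypothesis as two effects together, so the chance of showing both is a natural figure to look at. It is lower than either per-outcome power.

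**Working it through.** **Inputs (Section 4.5).** Interval: difference 22.6 − 18.0 = 4.6 h, SDs 6.8 and 8.2, so the variances sum to 46.24 + 67.24 = 113.48. Satisfaction: difference 1, SD 2 in each arm, variances sum to 8. Alpha 0.02, power 80%, 1:1 allocation, factors 1.15 and 0.9, N = 210. Sidedness is not stated. Two-sided testing is inferred because it reproduces the 54 (one-sided 0.02 would give about 45).

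**The plan's own figures.** n per arm = (2.326 + 0.842)² × (sum of variances) / (difference)².
- Interval: 10.036 × 113.48 / 21.16 = 53.8, so 54.
- Satisfaction: 10.036 × 8 / 1 = 80.3, so 81.
- Inflated: 54 × 1.15/0.9 = 69 and 81 × 1.15/0.9 = 103.5.

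All match the protocol.

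**Effective size.** 105 × 0.9 = 94.5 evaluable per arm. With the rank-test allowance fully used, 94.5/1.15 = 82.2.

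**Power per outcome at 82.2 per arm (normal approximation).** The expected test statistics are 4.6/√(113.48/82.2) = 3.91 and 1/√(8/82.2) = 3.20.

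| Two-sided level | Interval | Satisfaction |
|---|---|---|
| 0.02 | 94.4% | 81.0% |
| 0.025 | 95.3% | 83.2% |
| 0.04 | 96.9% | 87.5% |
| 0.05 | 97.5% | 89.3% |

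Using the t distribution lowers these by less than one percentage point.

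**Both outcomes, zero correlation.**
- Split at 0.02: 0.9439 × 0.8102 = 76.5%.
- Split at 0.025 (exact Bonferroni for 0.05): 0.9528 × 0.8324 = 79.3%.
- Holm at 0.05 needs both p values below 0.05 and at least one below 0.025: 0.9747 × 0.8934 − (0.9747 − 0.9528) × (0.8934 − 0.8324) = 0.8708 − 0.0013 = 87.0%.
- Holm at 0.04 (0.02, then 0.04), by the same formula: 0.8477 − 0.0016 = 84.6%.

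**Satisfaction alone under Holm at 0.05.** 0.8324 + (0.8934 − 0.8324) × 0.9528 = 89.1%, against 81.0% now.

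**Dependence on correlation.** The protocol gives no correlation between the two test statistics, so a range is assumed. Power for both, from a bivariate normal:

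| Correlation | Split 0.02 | Split 0.025 | Holm 0.04 | Holm 0.05 |
|---|---|---|---|---|
| 0 | 76.5% | 79.3% | 84.6% | 87.0% |
| 0.3 | 77.6% | 80.2% | 85.1% | 87.3% |
| 0.5 | 78.5% | 81.0% | 85.6% | 87.7% |
| 0.8 | 80.3% | 82.6% | 86.6% | 88.6% |

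**If the rank-test allowance is not used up (94.5 per arm).** The 0.02 split gives 84.0% to 86.2% over the same correlations. Holm at 0.05 gives 91.8% to 92.6%.

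**Where the gain comes from, at zero correlation.** From 76.5% to 79.3% (about 3 points) is the move from 0.02 to 0.025. From 79.3% to 87.0% (about 8 points) is the step-down. At a total of 0.04 the step-down also adds about 8 points (76.5% to 84.6%).

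**The case against.** The strongest reply is that nothing in Section 4.5 is wrong. Bonferroni at 0.02 controls the family error, here at 2 × 0.02 = 0.04, and the sample sizes follow from the inputs. This stands, and the point is one of efficiency only.

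A reader might go further and infer that the trial has 76% power where it claims 80%. The documents do not support that. The 80% is stated per outcome and is correct. The remark that 210 women suffice "to adequately cover for both primary outcomes" follows two separate calculations and naturally means each of them. Moreover, 76% is the low end of a range: it assumes zero correlation and a fully used rank-test allowance.

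A reader might also infer from the wording of Section 3.0 that success requires both effects. No section says so, and a Bonferroni split points the other way, since it is needed when either outcome alone may support a claim. On that reading the chance of at least one significant result is 98.9% at zero correlation. If both were required, no split would be needed, and testing each at 0.05 would give 87.1%. Holm gives practically the same joint power (87.0%) and still allows a valid claim on one outcome, so the recommendation does not depend on which reading is meant.

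Finally, the 0.02 appears only in the sample size section, and the testing rule may be set in a statistical analysis plan not seen here. Sizing at 0.02 is compatible with a later Holm analysis. That softens the point but does not remove it, because the only method that the protocol names is the less powerful one.

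**Conclusion.** The point holds as a free improvement, not as an error in the sample size. With 82 effective women per arm, replacing single-step Bonferroni at 0.02 with Holm at family alpha 0.05 raises power for satisfaction from about 81% to 89%. Power for both outcomes rises from about 76–80% to about 87–89%. The comparison is not at equal total alpha: it moves from 0.04 to the conventional 0.05, and on equal terms Holm alone adds about 8 points at zero correlation.

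The figures rest on the protocol's assumed effects and SDs, two-sided tests, correlations between 0 and 0.8, and full use of the rank-test allowance. If that allowance is not used, both starting point and result are higher (84–86% and about 92–93%). Holm's error control itself needs no assumption about the correlation.

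**What to change.** In Section 4.5 replace the Bonferroni wording with Holm's procedure at family alpha 0.05, and state the same rule in Section 6.1: test the smaller of the two primary p values at 0.025 and, if it is significant, test the other at 0.05. If the first is not significant, neither outcome is declared significant. Keep the sample size of 210. Beside the per-outcome powers, give the power for both outcomes together (about 87–89% on the planning assumptions), with the correlation range used.

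The cost is a few sentences, to be settled before outcome data are seen. No more women are needed and the family error stays at 0.05. The small downside is that Holm has no simple matching simultaneous confidence intervals, whereas Bonferroni does. The protocol should therefore say which confidence level will be reported for each primary outcome and that the Holm test decides significance.

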4.0 MATERIALS AND METHODOLOGY

4.1 STUDY DESIGN

Single centre, randomised controlled trial.

4.2 PLACE OF STUDY

Antenatal and labour ward, University Malaya Medical Centre, Kuala Lumpur.

4.3 POPULATION OF STUDY

Multiparous women planned for elective induction of labour for various indications admitted will be assessed for enrolment using the Eligibility Form.

Eligibility form

Inclusion Criteria

•	Multiparous women (at least 1 vaginal delivery ≥ 24 weeks)	
•	Age ≥ 18 years	
•	Gestational age of ≥ 37 weeks	
•	Singleton pregnancy	
•	Cephalic presentation	
•	Intact membrane	
•	Reassuring fetal heart tracing	
•	Absence of significant contraction ≥ 2 in 10 minutes	
•	Successful Foley insertion for IOL	
•	Bishop score ≤ 5	

Exclusion Criteria

•	History of caesarean delivery or hysterotomy/ uterine	
	perforation/ previous myomectomy	
•	Latex Allergy	
•	Estimated Fetal weight less than 2kg or > 4kg	
•	Known major fetal malformations	
•	Contraindication for vaginal delivery	
•	Patient who is suspected COVID 19 infection or COVID 19 positive	

4.4 METHODS

This is a randomised control trial involving multiparas at term (≥ 37 weeks) who are planned for IOL for various indications. Participant information sheet with be given to all potential recruits and any inquiries by the participants will be answered by the recruiting care provider. Written consent will be obtained from all participants.

All participants will undergo standard assessment by the care provider before their IOL; including their personal characteristics, obstetric assessment and fetal wellbeing (using a nonstress cardiotocogram) assessment.

Insertion of Foley Catheter

Participants will be positioned in the dorsal position. Bishop score will be ascertained during the vaginal examination prior to Foley insertion. A Foley catheter size 16F is then introduced through

the external os using either by digital or speculum method (at discretion of introducer). Once the tip of the catheter has passed the internal os by 4 to 5cm, the balloon will be inflated with 80ml of water and retracted so the balloon rests on the internal cervical os. The other end of the Foley catheter will be taped without tension to the medial aspect of the women's thigh. (19)

Randomisation

Randomisation will be performed and intention to treat revealed only after successful Foley insertion. Randomisation is done by opening the lowest number, sealed and opaque envelope that is available, assigned in strict order. Randomisation sequence will be generated using a random number generator at Random.org in random blocks of 4 or 8 sequence, generated by an investigator who is not involved in recruitment. Blinding is not possible due to the nature of the intervention.

Participants will be randomised into two trial arms: Foley removal following its insertion

1. at 6 hours

or

2. 12 hours

Trial will be closely monitored by the supervisors. Any serious adverse effects (SAE) will be reported to UMMC-MREC committee for discussion and review of the clinical trial.

Labour Induction Care

After catheter insertion, the patient will be monitored in the ward or labour suite with the cardiotocogram which is discontinued when reassuring. Standard care for Foley IOL in our centre is applied to both arms. They are allowed to ambulate. Analgesia is given upon request. Subsequent cardiotocogram is performed as indicated. Patients are transferred to labour and delivery suite if the catheter is spontaneously expelled before the designated 6 or 12 hours. The catheter is removed if spontaneous rupture of membrane occurs or there is clinical need as decided at the discretion of the care provider.

Upon Foley removal (or if spontaneously expelled before removal), a second Bishop score is recorded, artificial rupture of membranes performed, and oxytocin infusion is initiated according to standard IOL protocol (10 international units of oxytocin in 500mls of Hartmann solution, started at 6ml/hr [2 mU/min] and doubled every 30 minutes until 3–5/10 min regular painful contractions is achieved at which rate infusion rate is maintained to delivery if no untoward reaction, maximum dose at 96ml/hr [32 mU/min]). If artificial rupture of membranes is not possible or safe (i.e., fetal head at high station), oxytocin can be initiated prior to artificial rupture of membrane.

Failed ripening is diagnosed if Bishop score is ≤ 5 after removal of catheter. Patient will then be assessed and counselled by the care provider as standard care in these circumstances for medical induction with prostaglandin, oxytocin, another Foley or caesarean section. Standard care will be provided to all participants during their labour induction, intrapartum and postpartum. Care providers always have full discretion in deciding care to the participants' best interest.

Maternal satisfaction with the induction process will be assessed as soon as possible after delivery using the Visual Numerical Rating Scale scored from 0-10.

All date captured will be transcribed onto the Case Report Form.

4.5 SAMPLE SIZE CALCULATION

To calculate our sample size for the primary outcome, we obtained data from literature review on:

Primary outcome 1: Induction to delivery interval

Bleicher et al reported mean induction to delivery interval in the multiparous subgroup for 6 hours vs 12 hours double balloon placement as 18.0 hours with SD 6.8 vs 22.6 hours SD 8.2, p= 0.04 respectively, a mean reduction of 4.6 hours in favour of 6-hour placement.(14)

Using https://www.openepi.com/SampleSize/SSMean.htm and applying alpha of 0.02 (Bonferroni correction for 2 primary outcomes), t test, 80% power, 1 to 1 ratio, 18.0 hours with SD 6.8 vs 22.6 hours SD 8.2, 54 women are required per arm (total 104). Factoring in the possibility of non-normal data distribution requiring Mann Whitney U test application, we increase sample size by 15% and assuming 10% dropout, we plan to recruit $54 \times 1.15/0.9 = 69$ in each arm (N = 138 women)

For maternal satisfaction, assuming a 1-point difference in the 11-point 0-10 visual numerical rating scale (VNRS) to be clinically relevant. Using https://www.openepi.com/SampleSize/SSMean.htm and applying alpha of 0.02 (Bonferroni correction for 2 primary outcomes), t test, 80% power, VNRS standard deviation of 2 for both arms, 81 women are required per arm (total 162). Factoring in the Mann Whitney U test application as satisfaction score is ordinal, we increase sample size by 15% and assuming 10% dropout, we plan to recruit $81 \times 1.15/0.9 = 103.5$ in each arm (total of 207 women). We rounded the required sample size of participants up to N = 210 in total to adequately cover for both primary outcomes.

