6.1 STATISTICAL ANALYSIS

Data will be entered into SPSS statistical software. Normally distributed continuous data will be analysed with paired Student's t test. Chi square test will be used for categorical or nominal data and Mann- Whitney U test will be used on non-normally distributed or ordinal data.

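### The per-outcome alpha of 0.02 in Protocol section 4.5 does not match its Bonferroni label (0.05/2 = 0.025), and 54 per arm is totalled as 104 instead of 108; both slips are minor and the first is conservative

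*Protocol*

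**What the plan says.** Section 5.0 of the Protocol names two primary outcomes: the interval from Foley insertion to delivery, and maternal satisfaction with the induction process. Section 4.5 sizes the trial for each of them in turn.

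- **Interval to delivery.** The level is given as "applying alpha of 0.02 (Bonferroni correction for 2 primary outcomes), t test, 80% power", with 1:1 allocation. With means of 18.0 and 22.6 hours and SDs of 6.8 and 8.2, the result is "54 women are required per arm (total 104" in total. Inflating 54 by 1.15 and dividing by 0.9 gives 69 per arm, N = 138.
- **Satisfaction.** The level is given as "applying alpha of 0.02 (Bonferroni correction for 2 primary outcomes), t test, 80% power, VNRS standard deviation of 2 for both arms". For a 1-point difference the result is 81 per arm, 162 in total. The same inflation gives 103.5 per arm, 207 in total, rounded up to N = 210.

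Neither the family-wise level being divided nor the sidedness of the tests is stated. Section 6.1 names the tests to be used but gives no significance level.

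**The concern.** A Bonferroni correction divides a family-wise level by the number of tests. With two primary outcomes and the usual 5%, the result is 0.025. The protocol gives 0.02 and justifies it only as "Bonferroni correction for 2 primary outcomes". Either 0.02 was mis-derived from 5%, or the trial works at a family-wise level of 2 × 0.02 = 0.04 that it neither states nor explains.

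The alpha is an input to both sample sizes, including the one that sets N, so its derivation should be right. It is also the only significance level in the document. A reader who follows the label would take 0.025 as the level for each primary outcome, and a reader who follows the number would take 0.02. For a primary p value between the two, the protocol alone does not settle which reading applies, and that is better settled before the data are seen.

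The total of 104 is a separate arithmetic slip in the same calculation.

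**Working it through.** **Inputs, all from section 4.5.** Power 80%; 1:1 allocation; interval difference 22.6 − 18.0 = 4.6 hours, SDs 6.8 and 8.2; satisfaction difference 1 point, SD 2 in both arms; inflation × 1.15, then / 0.9; N = 210. Assumptions: two-sided tests, and a 5% family-wise level where 0.025 is used.

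**Formula (normal approximation).** n per arm = (SD1² + SD2²) × (z for 1 − α/2 + z for 0.80)² / difference².

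- Interval: (46.24 + 67.24) / 4.6² = 113.48 / 21.16 = 5.363.
- Satisfaction: (4 + 4) / 1² = 8.

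**Step 1: the plan's own figures, α = 0.02.** (2.3263 + 0.8416)² = 10.036.

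- Interval: 5.363 × 10.036 = 53.8, so 54.
- Satisfaction: 8 × 10.036 = 80.3, so 81.

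Both match the protocol. One-sided tests at 0.02 would give 45 and 68, so the calculation was two-sided. The inflation also reproduces: 54 × 1.15 / 0.9 = 69.0 and 81 × 1.15 / 0.9 = 103.5. So 0.02 is the level actually used, not a rounded display of 0.025.

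**Step 2: the same formula at α = 0.05/2 = 0.025.** (2.2414 + 0.8416)² = 9.505.

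| Outcome | Per arm at 0.02 | Per arm at 0.025 | 0.025 after × 1.15 / 0.9 | Total |
|---|---|---|---|---|
| Interval | 53.8, so 54 | 50.98, so 51 | 65.2, so 66 | 132 |
| Satisfaction | 80.3, so 81 | 76.04, so 77 | 98.4, so 99 | 198 |

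The planned N = 210 exceeds the larger total by 210 − 198 = 12 women.

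**Step 3: family-wise error.** At 0.02 each it is at most 0.02 + 0.02 = 0.04; for independent outcomes, 1 − 0.98² = 0.0396. At 0.025 each it is at most 0.05; for independent outcomes, 1 − 0.975² = 0.0494.

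**Step 4: power with N = 210.** After dropout and the Mann-Whitney allowance, 105 × 0.9 / 1.15 = 82.2 effective women per arm. For satisfaction, √(82.2 / 8) = 3.205.

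- At 0.025: 3.205 − 2.241 = 0.964, a power of 83.2%.
- At 0.02: 3.205 − 2.326 = 0.879, a power of 81.0%.

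For the interval, power is 95.3% at 0.025 and 94.4% at 0.02.

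**Step 5: sensitivity to the method.** With the noncentral t distribution, 0.025 needs 52.3 (53) and 77.3 (78) per arm. The larger becomes 78 × 1.15 / 0.9 = 99.7, so 100 per arm and 200 in total, still below 210. Satisfaction power is then 82.6% at 0.025 and 80.3% at 0.02. The conclusion does not change.

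**Step 6: the total.** 2 × 54 = 108, not 104. The 69 per arm is computed from 54, and N is set by satisfaction, so 104 is not used again.

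**The case against.** The strongest reply is that nothing in the trial is harmed. The 5% family-wise level is not in the document, and 0.02 per outcome is a valid, stricter choice. The stated sizes follow exactly from it, family-wise error is at most 0.04, and N is larger than 0.025 would require. All of this stands and sets the severity. It does not remove the mismatch: the only reason given for 0.02 is a correction that yields 0.025 from the conventional level, and no 4% level is mentioned anywhere.

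Three stronger readings are tempting, and the document supports none of them.

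- *The sample sizes are wrong.* They are right for the alpha stated. What is open to question is how that alpha was derived.
- *The decision threshold is wrong.* In section 4.5, 0.02 is a planning input to a sample-size calculator. No section says that p values will be judged against it.
- *The correction will not be applied, because section 6.1 gives no level.* A statistical analysis plan that is not shown may supply the level and the multiplicity rule, so this silence is not a defect in itself. Error rates computed for testing each outcome at 0.05 would presume that the analyst ignores a correction that section 4.5 names twice.

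A stepwise procedure such as Holm's would be a design preference; plain Bonferroni, which the protocol names, is valid.

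**Conclusion.** The point holds as a minor error. If the intended family-wise level is 5%, the Bonferroni level is 0.025, not 0.02, and the requirements before inflation are 51 and 77 per arm instead of 54 and 81. If 4% was intended, that needs to be stated and explained. The effect on the plan is about 12 women more than 0.025 requires (210 against 198), with no inflation of type I error and no loss of planned power. A reader might infer that the trial is wrongly sized or that its error control fails; the figures show neither.

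The total of 104 for 54 per arm is wrong whatever is assumed; it should be 108, with no consequence for N.

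The conclusion rests on a 5% family-wise level, which the protocol does not state; on two-sided tests, which the protocol does not state but its figures imply; and on the normal approximation, which reproduces the plan's own numbers.

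**What to change.** In section 4.5:

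- State the family-wise alpha and that the tests are two-sided.
- Use 0.025 per primary outcome and restate the requirements as 51 and 77 per arm before inflation (66 and 99 after it). Alternatively, keep 0.02 with 54 and 81, and state and justify the 4% family-wise level.
- Keep N = 210 and quote the resulting power for satisfaction: about 83% at 0.025, or about 81% if 0.02 is kept (normal approximation).
- Correct the total for 54 per arm from 104 to 108.

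Judge the two primary p values at the level chosen, and say so in section 6.1 or in the statistical analysis plan.

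The cost is a few sentences. Recruitment and procedures do not change.
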